The primary endpoint will be Time In Range (TIR) at D90, defined as the percentage of time spent with CGM glucose measurements at 70-180 mg/dL (including boundaries), during the last 14 days completed of CGM recording between D70 and D90 at the end of the study period.

For any of the 14 days to be eligible, \geq 70% of the data points have to be non missing. Full 24-hour periods available only will be used, thus excluding from the calculation all days with CGM sensor installation or desinstallation.

For data analysis and calculation of the TIR at baseline and at D90, gaps in the CGM recording for incomplete days will be imputed using a linear interpolation approach of the planned 14 days [51].

The primary endpoint will be computed at D90 for the full 24-h day. In a complementary way, the TIR will also be computed separately considering the diurnal period (from 06.00 H to 23.59 H) and the nocturnal period (from 00.00 H to 05.59 H).

VII.2 - SECONDARY ENDPOINTS

VII.2.1 - EFFICACY ENDPOINTS

- HbA1c absolute change from baseline: HbA1c will be assayed for all patients at baseline and
 D90. The absolute change from Baseline, i.e., HbA1c at D90 HbA1c at Dbaseline will be calculated for each patient.
- Absolute change of glucose variability from baseline:
- ullet The percentage coefficient of variation (%CV) will be computed at baseline (%CV_{Basl}) and D90 (%CV_{D90}), as well as the absolute difference (%CV_{D90}-%CV_{Basl}) for each patient [52]. For a given patient, the %CV_{Basl} will be calculated by dividing the Standard Deviation (SD) by the corresponding mean of the CGM recordings during the 14 days at the end of the selection period.

In the same manner, for each patient, the %CV_{D90} will be calculated by dividing the Standard Deviation (SD) by the corresponding mean of the CGM recordings during the last 14 days of the D70 to D90 period.

[figure not shown]
For each patient, $\%CV_{Basl}$, $\%CV_{D90}$ and the ($\%CV_{D90}$ - $\%CV_{Basl}$) difference will be computed 3 times:

- Considering the full 24-h day,
- ⇒ the diurnal period (from 06.00 H to 23.59 H),
- or the nocturnal period (from 00.00 H to 05.59 H) separately,

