- Absolute change of Time In Range from the 14 days completed CGM recording at the end of the selection period (baseline) to the last 14 days completed CGM recording from D70 to D90 at the end of the study period: time in range is defined in section VII.1 as the percentage of time spent in target range of glucose level (CGM measurements in 70-180 mg/dL (including boundaries)). At baseline, as well as from D70 to D90, any day of the considered period need to have ≥ 70% non missing data points to be eligible for the TIR computation. The absolute change in TIR from Baseline, i.e., D90-D0 will be calculated 3 times for each patient: (1) for the full 24-h day, (2) for the diurnal period (from

[figure not shown]

06.00 H to 23.59 H) and (3) for the nocturnal period (from 00.00 H to 05.59 H),

- Time below target range is defined as the percentage of time spent with CGM glucose measurements (1) <70 mg/dL, and (2) <54 mg/dL, during the last 14-day CGM completed recording from days 70 to 90. The time below target range will be computed for the full 24-h day, the diurnal period (from 06.00 H to 23.59 H) and the nocturnal period (from 00.00 H to 05.59 H) separately,
- Time above target range is defined as the percentage of time spent with CGM glucose measurements (1) >180 mg/dL, and (2) ≥250 mg/dL, during the last 14-day CGM completed recording from days 70 to 90. The time above target range will be computed for the full 24-h day, the diurnal period (from 06.00 H to 23.59 H) and the nocturnal period (from 00.00 H to 05.59 H) separately,
- Total daily insulin dose change from baseline to D90 (sum of basal and bolus insulin injection), Body weight absolute change from baseline (end of period of selection) to D90.

VII.3.1 - SAFETY PARAMETERS

Safety assessments are detailed in section VI.7.1.9. They include:

- Number of diabetes-related hospital admissions and their length of stay: the frequency of scheduled and unscheduled diabetes-related hospital admissions will be calculated for each study patient from baseline to D90.
- Number of hypoglycaemic events
- Number of diurnal hypoglycaemic events (i.e., occurring from 06.00 H to 23.59 H)
- Number of nocturnal hypoglycaemic events (i.e., occurring from 00.00 H to 05.59 H)
- Number of non severe hypoglycaemic events
- Number of severe hypoglycaemic events
- Number of severe diurnal hypoglycaemic events (i.e., occurring from 06.00 H to 23.59 H)

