Table 1: Estimated sample size needed to show the statistical significance of a difference Δ in TIR at D90 varying from 14% to 24% at the 5% level with a power of 90%

| Δ | Number of assessable patients (+10.0%) | % Loss | Number of patients to recruit by group |
|-----|--|--------|--|
| 14% | 31 | 25.0% | 42 |
| 15% | 27 | 25.0% | 36 |
| 16% | 25 | 25.0% | 34 |
| 17% | 21 | 25.0% | 28 |
| 18% | 19 | 25.0% | 26 |
| 19% | 17 | 25.0% | 23 |
| 20% | 16 | 25.0% | 22 |
| 21% | 15 | 25.0% | 20 |
| 22% | 14 | 25.0% | 19 |
| 23% | 13 | 25.0% | 18 |
| 24% | 11 | 25.0% | 15 |

X.2 - DATA SETS ANALYSED

X.2.1 - PATIENTS DATA SETS

The five following data sets analysed will be considered and exhaustively defined prior to the database lock:

- [1] The Selected data set will include all patients who signed an informed consent.
- [2] The Randomised Intention-to-treat (ITT) data set will include all patients who were randomised to study IMD.
- [3] **The Safety data set** will include all randomised patients continuing their study participation at the end of their initiation visit (V1).

- [4] The modified Intention-To-Treat (ITT) efficacy data set will include all patients from the safety data set with at least 3 days with ≥ 70% of non missing data points recording at baseline (selection period), as well as at the end of the study (planned from D70 to D90).
- [5] **The Per Protocol (PP) data set** will include all patients in the modified ITT efficacy data set who completed the 90-day study period without any major protocol deviation.

Safety analysis will be performed on the safety data set.

Efficacy parameters will be analysed in the modified ITT efficacy data set. The primary efficacy endpoint will also be analysed in the PP data set, the PP analysis serving as sensibility analysis.

According to ICH recommendation, modified ITT efficacy and PP analyses will be conducted according to the IMD assigned by the IWRS.

Safety analyses will be conducted according to the IMD actually equipped with rather than according to the IMD assigned.

The definition of the data sets analysed will be finalized during the final Data Review Meeting (DRM), before the database lock. During this DRM, all protocol deviations encountered throughout the study will be reviewed and their consequences on the efficacy evaluations performed will be evaluated.

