- and one table showing the number and percentage of patients with at least 1 metabolic system concomitant treatment with start date at the latest on the day before the initiation visit, by ATC system subgroups (ATC2, ATC3 and ATC4 codes).

X.3.3 - PRIMARY EFFICACY ENDPOINT ANALYSIS

The primary efficacy endpoint is the TIR at D90 for the full 24-h day (as detailed in section VII.1).

The primary analysis of this primary endpoint will be performed on the modified ITT efficacy data set (defined in section X.2.1). The TIR at D90 will be compared between both study groups using a parametric ANalysis of COVAriance (ANCOVA) model with 3 factors: HbA1c category level at baseline, TIR value at baseline as covariate and study group assigned by the IWRS.

This ANCOVA model corresponding to the primary analysis of the primary efficacy endpoint will allow testing the following set of hypotheses:

- H₀ (the null hypothesis of interest): mean TIR values at D90 are equal in the two groups,
- against H₁ (the alternative two-sided hypothesis): mean TIR values at D90 differ between the two groups.

This primary ANCOVA model will be repeated in a secondary supportive step, including the interaction between the HbA1c category level at baseline and the study group as fixed effect, if the study recruitment allows further exploration of the HbA1c category level effect on the TIR at D90.

If this interaction term is significant ($p \le 0.10$) and if it appears potentially relevant from a clinical point of view, further analyses and/or graphs might be produced to interpret this statistically significant interaction.

Both ANCOVA models with and without interaction term (*if relevant*) will be repeated on the TIR at D90 considering the diurnal period (*from 06.00 H to 23.59 H*) and the nocturnal period (*from 00.00 H to 05.59 H*) separately as supportive analyses of the primary efficacy endpoint.

Moreover, all 3 ANCOVA models with and without interaction term (*if relevant*) will be performed in the PP data set to check their robustness.

X.3.4 - SECONDARY EFFICACY ENDPOINTS ANALYSIS

The secondary efficacy endpoints will be analysed in the modified ITT efficacy data set.

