Each secondary efficacy endpoint will be summarised at each time point using descriptive statistics and compared between study groups using Cochran-Mantel-Haenszel chi-squared tests adjusted on the HbA1c level at baseline (2-categories stratification variable) or analyses of covariance with or without repeated measures (depending on the analysed parameter and its frequency of collection in both study groups) adjusted on the HbA1c level at baseline.

When appropriate, analyses based on CGM measures will be performed considering (1) the full 24-h day, (2) diurnal period (from 06.00 H to 23.59 H) and (3) nocturnal period (from 00.00 H to 05.59 H) separately.

When relevant, continuous, longitudinal endpoint data (e.g. HbA1c, Total daily insulin dose, body weight) will be analysed using the mixed effects model for repeated measures method based on the restricted maximum

likelihood for estimation with several prespecified fixed effects, including first-order interactions with time, and the corresponding endpoint as the dependent variable in the model. ANCOVA will be used for analyses of measures taken at a single time point post baseline in both study groups.

X.3.5 - SAFETY EVALUATION

Safety data will be tabulated descriptively by study group and assessment time, when relevant. Extent of exposure and Adverse Events will be tabulated in the Randomised ITT and the safety data sets (defined in section X.2.1). No statistical test will be performed.

X.3.5.1 - EXTENT OF EXPOSURE

Duration of the 4 study periods (Selection, Initiation, Run-in and Follow-up periods) and overall study duration will be tabulated (expressed in days) by study group (and globally), as both quantitative and categorical data.

Overall study duration is defined as the time interval between the actual date of the selection visit (*VO included*) and the actual date of the end of study visit (*V9 excluded*) whether the end of study occurred at the time of premature withdrawal or on visit date corresponding to D90 as planned, i.e., as the time interval equal to "date of end of study visit (V9) - date of selection visit (V0)".

X.3.5.2 - ADVERSE EVENTS (AES)

The time period for the recording of Adverse Events (AEs) is the time interval between selection (V0) and end of study (V9) divided in 2 periods, either before or after the initiation visit (V1). All reported AEs will be classified in one of these 2 periods, according to their start date.

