Unplanned hospitalisations whatever their reason (which will be reported as SAEs) will also be listed separately from all SAEs and they will be tabulated by study group, including the number and percentage of patients

hospitalised at least once during their study participation and the number of hospitalisations per patient (as both quantitative and categorical data).

X.3.5.3 - CLINICAL LABORATORY EVALUATION

In the safety data set, for each laboratory parameter (apart from HbA1c which is part of the secondary efficacy endpoints described in section X.3.4), laboratory results and their absolute variations from baseline (i.e., initiation visit (V1)) will be summarised as quantitative parameters using descriptive statistics by study group at the end of study visit (V9) planned to be performed at D90, using the observed case approach.

Number and percentage of patients above, below or within normal ranges in use in each laboratory involved will also be tabulated by study group for each parameter at study end.

A shift table will also be provided for each parameter at study end to depict the number and percentage of patients with post_baseline decreased laboratory values (from Within Normal Ranges to Below, from Above normal ranges to Within Normal Ranges or from Above normal ranges to Below), the number and percentage of subjects without changes (either always Within Normal Ranges or Above or Below) and the number and percentage of patients with post_baseline increased laboratory values (from Below to Within Normal Ranges, from Within Normal Ranges to Above or from Below normal ranges to Above) by study group.

X.3.5.4 - VITAL SIGNS, PHYSICAL FINDINGS AND OTHER OBSERVATIONS RELATED TO SAFETY

For systolic and diastolic resting blood pressure separately, quantitative descriptive statistics will be tabulated on the safety data set by visit planned and study group, using the observed case approach.

For each parameter separately, the absolute variations "post-initiation period – baseline (recorded at initiation visit (V1))" will also be tabulated by visit planned and study group.

[figure not shown]
X.3.5.5 - **CONCOMITANT TREATMENTS**

All concomitant treatments with start date at the earliest on the day of the initiation visit will be tabulated descriptively by study group in the safety data set using the WHO_DRUG dictionary and the Anatomical Therapeutic Chemical (ATC) classification. Three (3) tables will be provided:

[figure not shown]

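### HbA1c, body weight and insulin dose are analysed only in patients with enough end-of-study CGM data, so measured D90 values can be dropped by a post-randomisation sensor condition

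*Combined protocol and SAP*

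**What the plan says.** Section X.2.1 builds the modified ITT efficacy set from the safety set, keeping only patients "with at least 3 days with ≥ 70% of non missing data points recording at baseline (selection period), as well as at the end"; the second period is D70-D90. The synopsis gives the same CGM condition.

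Two places then apply this set to efficacy generally. Section X.2.1: "Efficacy parameters will be analysed in the modified ITT efficacy data set". Section X.3.4: "The secondary efficacy endpoints will be analysed in the modified ITT efficacy data set".

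Three of the secondary efficacy endpoints in section VII.2.1 are not defined from CGM readings:

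- HbA1c change, where "HbA1c will be assayed for all patients at baseline and" D90;
- "Total daily insulin dose change from baseline to D90 (sum of basal and bolus insulin injection";
- the change in body weight up to D90.

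Section VI.6.1 has laboratory tests, including HbA1c, and body weight taken at the end-of-study visit in both groups. No section names another analysis set for comparing these endpoints. Section X.3.5.3, which analyses laboratory results in the safety set, covers each parameter "apart from HbA1c which is part of the secondary efficacy endpoints described in section X.3.4". Section X.3.4 adds that "continuous, longitudinal endpoint data (e.g. HbA1c, Total daily insulin dose, body weight) will be analysed using the mixed effects model for repeated measures" when relevant, with ANCOVA for a single post-baseline time point.

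**The concern.** A CGM-completeness rule makes sense for time in range, time below and above range and %CV, which cannot be computed without the sensor. HbA1c and weight can. Applying the rule to them discards values that the trial has measured.

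The rule also acts after randomisation. Inclusion criterion 4 (section IV.1.2) already requires 14 completed days of baseline CGM, so nearly all exclusions must come from the D70-D90 half.

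Missing CGM in that window can mean different things in the two arms. In the investigational arm the loop runs on the sensor, so absent CGM may mean the system was not in use. Controls wear a blinded CGM for 20 days at the end of follow-up (sections V.3 and VI.5.3), and missing data there say nothing about how their insulin was delivered. The exclusion may therefore be related to outcome, and differently by arm.

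HbA1c matters most here. Section I.1.5.4 describes it as the established surrogate marker and notes that the FDA had not accepted TIR as proof of efficacy. It is the natural check on an open-label, CGM-based primary result. Restricted to patients who already passed the CGM condition, it cannot show whether that selection matters.

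**Working it through.** **1. The plan's own numbers.** Inputs from section X.1: difference 17, SD 16, two-sided alpha 5%, power 90%, 10% added for adjustment, 25% non-evaluable.

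- n per group = 2 × (16²/17²) × (1.960 + 1.282)² = 18.6, rounded up to 19.
- 19 × 1.10 = 20.9, rounded up to 21.
- 21 / 0.75 = 28 per group, 56 in total, 42 evaluable.

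The stated figures reproduce and are not in dispute. They concern TIR; the documents give no sample-size figure for HbA1c, weight or insulin dose.

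**2. How many patients could be affected.** The plan allows 56 − 42 = 14 patients outside the evaluable set. It does not say how many of them would still have a D90 HbA1c or weight, so the range is 0 to 14.

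**3. Effect on precision.** For equal arms and a common SD s, the standard error of the group difference is s × √(2/n), with n per arm. With N patients in total once the CGM condition is removed, the standard error under the plan is larger by the factor √(N/42).

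| Patients recovered | N | Factor | Status |
|---|---|---|---|
| 0 | 42 | 1.00 | lower bound |
| 2 | 44 | √(44/42) = 1.02 | assumption |
| 4 | 46 | √(46/42) = 1.05 | assumption |
| 14 | 56 | √(56/42) = 1.155 | ceiling: no D90 value is missing |

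**4. Where in the range.** Two features point to the lower part. Section III describes the 25% as estimated dropout, and section IV.4 does not keep data collected after a patient withdraws, so a patient lost that way would generally have no D90 value to recover. The threshold is also only 3 valid days within D70-D90.

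**5. Whether another rule rescues these endpoints.**

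- The per-protocol set is a subset of the modified ITT set and is used only for the primary endpoint.
- The observed-case wording in section X.3.1 names no analysis set, so it does not override X.3.4.
- The mixed model does not help, because the patients are removed before it is fitted.
- The safety-set laboratory tables leave HbA1c out.

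**The case against.** The strongest reply is that few patients will be affected, on endpoints that carry no confirmatory weight. Each sensor lasts at most 10 days (section V.1.2), so a 20-day control recording spans at least two sensors and one failure need not exclude the patient. Section V.2 provides a hotline and device replacement within 12 hours. An investigational patient who stops the sensor may be withdrawn for non-compliance under section IV.4 and then have no D90 HbA1c. Section X.3.1 declares everything beyond the primary analysis exploratory and descriptive.

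All of this stands as an argument about size. It does not remove the rule. Section IV.4 lists device discontinuation as a withdrawal reason only for the initiation and run-in periods, so a patient who stops the sensor later can still reach the final visit with a valid HbA1c. Descriptive results are also better described in everyone who was measured.

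Two further objections stand. Requiring both a baseline and an end-of-study value is still an analysis of available data, so it does not remove selection by dropout. And for insulin, section VI.7.1.4 lists trade name and dates but no dose, so the text does not show that total daily dose is available for every patient who lacks CGM or pump data.

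Finally, section X.2.1 leaves the data sets to be finalised at the data review meeting, and section X.3 announces a separate SAP approved after it. The final rule may differ, but the current text gives no sign of that.

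**Conclusion.** The point holds as a matter of analysis-set definition. Measured HbA1c and weight values can be excluded by a post-randomisation CGM condition that these endpoints do not need, and the only sensor-free measure of glycaemic control inherits the primary endpoint's selection. The precision cost is a factor between 1.00 and 1.155, or 1.02 to 1.05 if 2 to 4 patients are recovered. These figures assume equal arms, a common SD and 42 patients in the modified ITT set. Any bias cannot be sized from the documents, and its direction is not established.

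Four stronger readings are tempting and are not supported:

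- A reader might expect intervals 8% to 15% wider, from √(49/42) = 1.08 and √(56/42) = 1.155. The first assumes that half of the 14 have a D90 value, for which the documents give no basis. The second assumes that all do, which is hard to square with a 25% described as dropout.
- A reader might infer that the excluded patients are the worst device users. That is possible, but no figure supports it.
- A reader might call the sensor condition irrelevant to these endpoints. It is irrelevant to measuring them; whether it is unrelated to their values is unknown.
- A reader might take HbA1c to be the only efficacy endpoint that needs no CGM. Weight and insulin dose are others; HbA1c is the only one that measures glycaemic control.

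The primary conclusion is unaffected. This is an inexpensive improvement to exploratory analyses.

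**What to change.** In sections X.2.1 and X.3.4, limit the CGM-completeness condition to the CGM-derived endpoints: TIR, time below range, time above range and %CV.

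Analyse HbA1c and body weight, and total daily insulin dose where it is recorded, by assigned group in all randomised patients with available baseline and end-of-study values. Show the modified ITT result as supportive. This also lifts, for these endpoints, the requirement of still being in the study at the end of V1, so the new sentence should say so openly.

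Report by arm the number of patients who have a D90 HbA1c but fail the CGM condition. That count shows directly whether the issue mattered.

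The cost is one sentence in each section and one line in the disposition table. No new HbA1c or weight data are needed. For insulin dose, the team should first confirm what is recorded in patients without CGM or pump data. The change should be made before the data review meeting fixes the analysis sets.
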